## 4 STUDY POPULATION AND STUDY PROCEDURES

### 4.1 Inclusion and exclusion criteria, rationale for study population

Patients hospitalized with acute heart failure with reduced LVEF, poly-mediated from the Departments of General Internal Medicine and Cardiology of a Swiss university hospital in Geneva, will be included.

This is a very frequently hospitalized patient population on these services. Heart failure was the leading cause of hospitalization in general internal medicine in 2019 and is currently in the top 10 reasons for hospitalization despite the appearance of SARS-Cov-2 infection and its respiratory complications. There are other reasons why we chose this population to evaluate the impact of hospital-based education:

- There is currently no therapeutic education offer for hospitalized heart failure patients at the HUG compared to other populations such as diabetic patients, patients suffering from chronic obstructive pulmonary disease or patients who have had a STEMI with the ELIPS program.
- Not all patients with this pathology can be followed in the hospital by the interdisciplinary heart failure team of the HUG.
- The evidence-based medicine guidelines written by the European Society of Cardiology have been updated in 2021. They will impact the drug management of heart failure patients. They encourage the introduction of medication in patients with reduced heart failure (LVEF < 40%) and also in patients with slightly reduced function (41-49%). In addition, the introduction of recent first-line drug therapies such as Entresto® and renal SGLT-2 co-transporter inhibitors (Forxiga® or Jardiance®) will result in changes in prescribing and the need for closer monitoring of adverse events. The reinforcement of a multi and interdisciplinary management is also strongly encouraged in these latest recommendations. Our project is in line with these recommendations.
- This population is at risk for multiple cardiac decompensations and potentially avoidable healthcare consumption (rehospitalization, unplanned physician visits, or emergency room visits).
- Clinical practice shows that many hospitalized patients with heart failure do not know what their disease is and how it is treated. A small field survey on the information needs of these patients was conducted with about ten patients in the General Internal Medicine Department of the HUG in 2021 and showed that patients were not able to define their heart failure disease, nor to explain the role of their medication and that they were eager to obtain more targeted information on their disease and their medication.

All hospitalized patients with left heart failure with a decreased LVEF  $\leq 40\%$  (HFrEF) as well as those with LVEF between 41 and 49% (HFmrEF) only if treated with heart failure specific drug therapy will be approached to introduce them to the study provided they meet the inclusion criteria.

The vast majority of the heart failure population is elderly and at risk for cognitive impairment. This may negatively influence the results of this score and bias the real impact of the educational intervention. To address this issue, only patients without cognitive impairment will be included. To identify the cognitive status of each patient, the following items will be analyzed in order of priority.

- Judgment of the internal physician in charge of the patient.

- If the physician is in doubt about the patient's cognitive status, a Mini Mental Status (MMS) and a clock test (only if the MMS is greater than 24) will be performed by the investigator or a geriatric liaison nurse attached to the General Internal Medicine Service. Cognitive impairment is possible if MMS score  $\leq 24$  and if MMS  $\geq 24$  and clock test score  $\leq 7$ .

Patients hospitalized at the University Hospital of Geneva meeting the following inclusion criteria are eligible for the study:

- Hospitalized in the Department of General Internal Medicine or Cardiology for decompensated heart failure (also called cardiac decompensation, acute heart failure)
  - o with lowered left ventricular ejection fraction (LVEF) ( $\leq 40\%$ ) of any origin;
  - o with slightly reduced left ventricular ejection fraction (LVEF) (41-49%) only if treated with the specific drug therapy for heart failure

Or

- Hospitalized in the Department of General Internal Medicine or Cardiology and presenting during hospitalization with decompensated heart failure (also called cardiac decompensation, acute heart failure)
  - o With lowered left ventricular ejection fraction (LVEF) ( $\leq 40\%$ );
  - o with slightly reduced left ventricular ejection fraction (LVEF) (41-49%) only if treated with the specific drug therapy for heart failure
- Stability of clinical condition as judged by the internal physician in charge of the patient including:
  - o hospitalization in acute unit only
  - o absence of oxygen dependence or oxygen dependence outside of heart failure
  - o weight loss initiated if diuretic is present
- $\geq 2$  medications to treat heart failure
- $\geq 18$  years
- Full capacity of discernment
- Absence of cognitive impairment (notion of cognitive impairment in the patient record or judgment of the internal physician in charge of the participant or MMS  $\leq 24$  / MMS  $\geq 24$  and clock test score  $\leq 7$ )
- Ability to speak, understand and read in French
- Has a personal telephone (mobile or landline)
- Signed the consent form (Appendix 8)

The presence of any of the following criteria will result in the exclusion of the participant:

- Inability to follow study procedures, e.g., due to a somatic medical condition such as confusion, language problem, psychological disorder, cognitive impairment)
- Institutionalized persons (e.g., nursing home, home for the aged)
- Asylum seekers, homeless people, prisoners
- Person under guardianship
- Short life expectancy (patient at end of life or comfort care)

#### **4.2 Recruitment, screening and informed consent process**

The investigating pharmacist will identify each working day (Monday to Friday) the patients hospitalized for cardiac decompensation in the Internal Medicine and Cardiology Departments of the University Hospitals of Geneva by means of the computerized patient records.

A computerized rule has been designed by the HUG Pharmacy to highlight the patients of the Services of General Internal Medicine and Cardiology presenting in their medical problems a cardiac decompensation.

The pharmacist will analyze the most recent echocardiography report for each of these patients to determine the LVEF value of the heart. This identification step can be completed by the weekly lists sent by e-mail to the hospital cardiologists and to the investigating pharmacist, of the patients who have received a cardiac echocardiography (transthoracic and/or transoesophageal) by the Cardiology Department.

The eligibility of patients with heart failure with diminished LVEF will be assessed by analysis of the computerized patient records, applying the inclusion and exclusion criteria, and by discussion with the internal physician in charge of the patient, particularly with regard to the capacity for discernment. If there is no notion of cognitive disorders in the patient's file, this will be discussed with the internal physician in charge of the patient to find out whether or not the patient has cognitive disorders. If the physician suspects it, an MMS test and possibly a clock test will be performed by the investigating pharmacist or by a nurse from the geriatric liaison team. If a patient has an MMS score of less than 24 or an MMS score of more than 24 with a clock test score of less than or equal to 7, he or she may have cognitive impairment and cannot be included.

For all eligible patients, the investigating pharmacist will introduce them to the study on the second day of hospitalization. He will explain the nature of the study, its objectives, the procedures involved, the expected duration and the potential risks and benefits of participating. He will explain that the study is composed of two arms and that it is randomly determined in which group each participant is assigned.

Each participant will be informed that participation is voluntary and that he/she may withdraw from the study at any time. Participation in or withdrawal from the study will not affect his or her therapeutic management. They will also be informed that their medical records will be consulted by the investigating pharmacist.

All participants will receive a study information sheet and a consent form to sign in order to make an informed decision about whether or not to participate in the study (Appendix 8). The patient will be given 24 hours to decide whether or not to participate in the study. Formal consent will be obtained by collecting the consent form signed by the participant. It will be countersigned by the investigator or his representative. The consent form will be kept in the study file and a copy given to the participant. As soon as the patient's informed consent to participate is obtained, an appointment will be scheduled with the patient for the first stage of the intervention.

Each eligible participant included in the study will be assigned an authentication number in order to anonymize their data and an electronic case report form (eCRF) or observation sheet will be created.

A randomization list by random size block will be established beforehand by the HUG methodological support unit. This list will be held by the pharmacist in charge of the clinical trials, [name], within the HUG pharmacy (person external to the project). Randomization will be automated in the Clinical Trial Data Management System CDMS RedCAP™ and activated for each new participant who will require the creation of a new eCRF. In case of malfunction of this software, [name] will be notified by the system and will be able to assign each participant to the arm according to the predefined list.

The investigator will identify the assigned arm for each participant after collecting the patient consent form. The investigator will schedule the therapeutic education intervention on the same day for the participants in the intervention arm and collect the pre-test data from the participants.

Follow-up up to 1 month post-discharge involves a potential risk of loss of participants. Some may withdraw from the study. These cases will be reported as, "withdrawal of informed consent" or "loss to follow-up". Data from patients who die during the study will be considered for final data analysis.

Participants will not be compensated for their involvement in the study. They will have the right to request the final results of this study.

### 4.3 Study procedures

Duration of inclusion: 52 weeks (June 01, 2022 to May 31, 2023)

[figure not shown]
End of follow-up: 1-2 months (end in 08/2023)

**Table 1: Study Schedule**

Recruiting																			
Evaluation at 1 month post-hospitalization																			
											Analysis of the results								
Sept.22	Oct.22	Nov.22	Dec. 22	Jan. 23	Feb. 23	Tue 23	Apr. 23	May.23	Jul. 23	Jul . 23	Aug.23	Sept.23	Oct. 23	Nov .23	Dec.23				

## Conduct of the study

## Data collected

Baseline patient information, medical data, heart failure data, laboratory data, vital parameter data, medication data will be collected for each patient included in the study once the consent form is completed. Other study data will be collected for pre-testing after randomization.

The data collected for the intervention group will be collected after the teaching interview, during the telephone call upon discharge and for the post-test at 1 month after discharge. Data for the control group will be collected for the post-test at 1 month after discharge.

All these data are presented in Table 2.

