Study procedures	
Each working day, the investigator will identify all patients with heart failure with a lowered left ventricular ejection fraction (LVEF) and hospitalized for cardiac decompensation at the HUG. He will assess whether they meet the eligibility criteria for this study. The investigator or a trained clinical research associate (CRA) will come and present the study to the eligible patients by giving them the information sheet and the consent form to sign if they agree to participate. They will be given at least 24 hours to think about whether they want to participate. Once the patients are included (eligibility criteria validated and consent signed), they will be randomly assigned to the intervention or control group according to the randomization list.
 
For patients in the intervention group, the therapeutic education intervention will be scheduled on the same day or the next day. The pre-test questionnaires (knowledge, beliefs, and adherence) will be given to them before the educational intervention. The post-test questionnaires and satisfaction survey will be given to the participants directly after the intervention. A second discharge interview will be organized shortly before final discharge from the general internal medicine or cardiology department. A call within 7

	
days of discharge will be made and an assessment at 1 month of hospitalization of the primary (knowledge) and secondary (beliefs, adherence, satisfaction, consumption of unplanned care) endpoints will be made either by e-mail, postal mail, or telephone call by the CRA only.
 
For patients in the control group, the pre-test questionnaires on knowledge, beliefs and adherence will be given to them on the same day or the day after inclusion. A post-test evaluation of knowledge, beliefs, adherence and rate of consumption of unplanned care will be performed at 1 month after hospitalization.

Study duration and Schedule	
12 months
 
Planned from 09/2022 for inclusion of first participant
 
Planned to 09/2023 for inclusion of last participant

Investigator(s)	[name] candidate, HUG Pharmacy
Study Center	
University Hospitals of Geneva
 
[name]
 
[name]

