 28 For example for question n° 2: 1 point if predefined keyword present; 0,5pt if partial keyword  
 29 but general concept correct; 0 pt otherwise.

30  
 31 The final score can vary from 0 (no knowledge) to 17 points (excellent knowledge).  
 32 The questionnaire has never been used in an experimental context or for psychometric  
 33 analysis. There is no threshold to say that a patient has good knowledge or not.  
 34 It was developed by an internal pharmacist and an assistant pharmacist trained in TVE. It is  
 35 based on educational objectives derived from educational sessions with patients and meetings  
 36 with two patient partners from the HUG (Appendix 2). It was previously evaluated with them  
 37 and on three occasions with a group of hospitalized heart failure patients (10 patients per  
 38 version of the questionnaire).

39  
 40 To determine a first basic level of knowledge of the heart failure patients hospitalized at the  
 41 HUG, the final version of the questionnaire was tested with 10 patients who had not received  
 42 any educational intervention. This analysis shows that:

- 43 • The average baseline score is 7.95 pts out of 17.00pts (with a standard deviation of  
 44 2.67) or 46.76% of correct answers;
- 45 • The median score of 8.25pts out of 17.00 pts (min. 4; max. 13) or 48.53% of correct  
 46 answers.

47  
 48 In this clinical study, we wish to assess the level of knowledge of the intervention group before  
 49 the teaching interview, directly after the teaching interview, and at 1 month after the  
 50 participant's discharge from the hospital.

51 This study includes a control group in order to evaluate the real effect of the therapeutic  
 52 teaching intervention. The level of knowledge of the control group will be evaluated at inclusion  
 53 for the pre-test and at 1 month after hospitalization for the post-test.

54

1  
2 Secondary endpoints included differences in medication belief and adherence scores and the  
3 difference in the rate of unplanned care use between the two groups at 1 month post-  
4 hospitalization.

5  
6 They also focused, for the intervention group, on the difference in belief and therapeutic  
7 adherence scores between the period before the educational intervention during  
8 hospitalization and the period following this intervention, i.e., one month after hospital  
9 discharge.

10 Four additional endpoints will be assessed after the pharmaceutical intervention with the study  

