50	Heart failure medication list (hospital discharge)	Medical record	 Diuretic  Beta-blocker  IECA/ARA  ARNI  Aldosterone antagonist (ARM)  SGLT2 inhibitor  Ivabradine  Digoxin  Vericiguat
51	Medication management in the home	Patient interview	 Autonomous  Nursing care  Pharmacy  Caregivers
52	Medication management tool	Patient interview	 Paper Medication Plan  Electronic Medication Plan  Weekly/Plus  Daily unit dose sachet  Unit discount by the pharmacy  Other
53	Frequency of visits to your regular pharmacy	Patient interview	 Several times a week  1 time per week  2-3 times a month  1 time per month  1 time every 2-3 months  2 times a year  1 time per year  Never
54	Quality of the relationship with your city pharmacist	Patient interview	 No particular relationship  Wrong  Neither good nor bad  Good  Very good
Pre-test data			
55	Knowledge Questionnaire	Patient interview	Answer for each question (detailed in the documents specific to the questionnaires)
56	Score	Calculation	Value:
57	Belief questionnaires	Patient interview	Answer for each question (detailed in the documents specific to the questionnaires)

58	Need score	Calculation	Value:
59	Concern score	Calculation	Value:
60	Differential score	Calculation	Value:
61	Membership questionnaire	Patient interview	Answer for each question (detailed in the documents specific to the questionnaires)
62	Membership score	Calculation	Value:
Post-interview FTE data (for intervention group only)			
63	Knowledge Questionnaire	Patient interview	Answer for each question (detailed in the documents specific to the questionnaires)
64	Score	Calculation	Value:

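### The baseline knowledge score is taken after randomisation by an investigator who knows the arm, and no available text masks the scoring of the open items: a possible bias that is cheap to close

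*Combined protocol and SAP*

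**What the plan says.** **Order.** In the Synopsis (Study procedures), once eligibility is confirmed and consent signed, "they will be randomly assigned to the intervention or control group according to the randomization list"; the pre-test follows. For controls the pre-test questionnaires "will be given to them on the same day or the day after inclusion". Section 4.2 states: "The investigator will identify the assigned arm for each participant after collecting the patient consent form". The same person then schedules the teaching and collects the pre-test data. Section 4.3 (Data collected) gathers the other baseline data on completion of consent, but for the questionnaires says: "Other study data will be collected for pre-testing after randomization". Section 4.2 ties the automated REDCap randomisation to the creation of a new eCRF.

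**Who handles the form.** Section 4.3 (Assessment of the level of knowledge) has patients complete the questionnaire themselves, with the pharmacist's help where needed. Section 3.4 has the pharmacist investigator deliver the teaching. Section 3.2 also lets the research assistant hand out the hospital questionnaires.

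**Scoring.** Section 3.2 describes 17 questions: 14 closed and 3 open. The open ones are scored subjectively against keywords. The example, question 2, gives "1 point if predefined keyword present; 0,5pt if partial keyword" with a correct general concept, and 0 otherwise. Table 2 records answers and score as separate entries. No available text names the scorer or says whether the arm is hidden, at the pre-test or at 1 month.

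**Use.** Section 5.1 (Primary analysis) adjusts the 1-month score for this baseline. Sections 5.1 and 5.2 also substitute it for a missing 1-month score.

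**The concern.** Adjustment for baseline is safe when allocation cannot have influenced the baseline. Here the person collecting the covariate knows the arm, may help with the answers, and will teach the intervention patients. Whoever scores the open items may also know the arm. Even a small, unintended difference in help or leniency between arms would enter the primary estimate with the opposite sign, and the ANCOVA would treat it as a true baseline difference. The same open items are scored again at 1 month, where a difference between arms would enter the primary estimate at full weight.

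**Working it through.** The plan states no figure for this issue, so there is none to reproduce. What follows shows how large the effect would be under stated assumptions.

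**Inputs from the plan.** SD 2.67 and target difference 2.39 (section 5.1, Sample size). 45 per group, from 40 / 0.9 = 44.4, rounded up. 10% loss to follow-up. Two-sided alpha 5%.

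**Assumptions, not in the plan.** Slope s of the 1-month score on baseline: 0.3 to 0.7. SD 2.67 at both times. Shift d in the measured baseline of one arm: 0.25 or 0.5 points.

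**Baseline shift.** Bias of the adjusted difference is about −s × d, or −0.9 × s × d if 10% of outcomes are carried forward. The standard error is about 2.67 × √(1 − s²) × √(2/45). With r = s × d / SE, type I error is about P(Z > 1.96 − r) + P(Z < −1.96 − r).

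| s | SE | d = 0.25: bias, r, type I | d = 0.5: bias, r, type I |
|---|---|---|---|
| 0.3 | 0.537 | 0.075, 0.14, 5.2% | 0.15, 0.28, 5.9% |
| 0.5 | 0.487 | 0.125, 0.26, 5.8% | 0.25, 0.51, 8.1% |
| 0.7 | 0.402 | 0.175, 0.44, 7.2% | 0.35, 0.87, 14.0% |

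Simulation of the same model (40,000 runs per setting) agrees: 5.1-7.1% and 5.6-13.7% without carry-forward; 5.2-7.0% and 5.5-12.5% with 10% carried forward.

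**What such shifts would take.** If all three open items use half-point steps as question 2 does, and scoring is the only route, then d = 3 × 0.5 × q, where q is the share of open answers in one arm moved by one step. A shift of 0.25 needs q = 1/6; 0.5 needs q = 1/3.

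**Power.** With a true effect of 2.39, d = 0.5 and s = 0.3, the estimate falls to 2.39 − 0.15 = 2.24. Then 2.24 / 0.537 = 4.17, and P(Z > 1.96 − 4.17) is about 98-99%. Even at a 1-point shift the lowest simulated power is about 96%, or 93% with 10% carried forward.

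**Scoring shift at 1 month.** A shift d in the outcome enters at full weight. For d = 0.5, r = 0.5 / SE = 0.93, 1.03 and 1.24, giving type I error of about 15%, 18% and 24% (about 15-23% in simulation). If a scorer were equally lenient to one arm at both times, the net bias would be d − s × d = d(1 − s): 0.35, 0.25 and 0.15 points. Masking only the pre-test would raise that to the full 0.5.

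**Unadjusted comparison.** A t-test on the 1-month score does not use the baseline as covariate. Against a baseline shift its type I error is about 5%, and at most about 5.6% with 10% carried forward, because carried values still bring in about 0.1 × d.

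**The case against.** The opportunity for bias is limited. Patients complete the form themselves, 14 of the 17 questions are closed, the example for open scoring uses a predefined keyword, and sections 3.4 and 4.3 place the pre-test before any teaching. A 0.25-point shift barely changes the error rate. All of this stands. It bounds the problem without removing it: help is not confined to the open items, and the documents give no reason for randomising first.

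Some stronger inferences are not supported:

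- *That the baseline is biased.* Nothing shows this. The teaching cannot contaminate the pre-test, and neither d nor the slope is given.
- *That the plan has no protection.* Section 5 provides a t-test for differences in continuous outcomes between the groups. This can fairly be read as covering the 1-month knowledge score, although the text does not say so.
- *That the trial has no masked scoring.* Appendix 1 and Figure 1 were not available, and Table 2 refers to separate questionnaire documents. Only the available text is silent.
- *That error rates could be several times nominal.* A 1-point shift with s = 0.7 would give up to 39%. Through scoring alone it would need two in three open answers in one arm moved by a half-point step, and nothing in the documents supports that.
- *That the plan contradicts itself on timing.* Section 3.2 says "The level of knowledge of the control group will be evaluated at inclusion". This is ordinary shorthand and is compatible with a pre-test shortly after allocation.

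**Conclusion.** The sequencing weakness is real and worth correcting. The primary covariate, which is also the carried-forward value, is obtained after allocation by someone who knows the arm, and no available text masks the scoring of the three open items. The bias is possible rather than demonstrated, and its size and direction are unknown. Under the assumptions above, type I error would be about 5-7% for a 0.25-point baseline shift and about 6-14% for 0.5 points, while the ability to detect 2.39 points is little affected. The figures depend on the assumed slopes and shifts, on equal SDs, and on the pilot SD from 10 patients. Masked scoring has to include the 1-month answers, because that route carries the greater weight.

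**What to change.** 1. In the Synopsis (Study procedures), section 4.2 and section 4.3 (Data collected), set the order as consent, pre-test completed and locked, then randomisation. Move the REDCap trigger from eCRF creation to locking of the pre-test answers. Enter paper forms before allocation is released.
2. In section 3.2, state that the open items at all time points, including 1 month, are scored from coded answers with the arm hidden, by a person already on the study team. Code each answer sheet separately and hide the time point as well, because only the intervention group has a test directly after teaching.
3. If any patient has already been randomised under the present order, state in section 5 that the planned t-test covers the 1-month knowledge score, and report it as an unadjusted sensitivity analysis. It guards against a baseline shift, not against a scoring shift at 1 month.

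Cost: sample size and alpha are unchanged, and no new staff or forms are needed. Allocation comes slightly later. A patient who needs time for three questionnaires may require a second bedside visit from an investigator who works part-time on the project (section 5.1). The scoring is a small added task. The reorder may count as a substantial change needing prior ethics approval (section 6.4).
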